## Study design

This randomized split-mouth clinical trial included 13 systemically healthy adults with a total of 65 papilla deficiencies in the aesthetic zone. The study was approved by the Altınbaş University Ethics Committee. All participants provided written informed consent.

Inclusion criteria required  $\geq 2$  papillae classified as Papilla Presence Index (PPI) class 2 or 3, probing depths  $\leq 3$  mm, and plaque and bleeding scores below 15%. Exclusion criteria included PPI class 4, diastema, active periodontal disease, smoking, pregnancy, systemic conditions influencing healing, anticoagulant use, and previous surgical papilla reconstruction.

For each participant, one side was randomly assigned HA and the contralateral side i-PRF. The clinical examiner underwent intra-examiner calibration until repeated measurements were consistent within  $\pm 1$  mm. Outcome assessments were performed by a blinded examiner.

For i-PRF sites, 10–20 mL of venous blood was collected into plastic tubes and centrifuged at 700 rpm for 3 minutes. The upper orange plasma layer was aspirated and transferred to 1-mL insulin syringes. Injections were delivered within 5 minutes to ensure liquid consistency before polymerization.

All treatments were performed with buccal infiltration anesthesia. HA or i-PRF (0.1–0.2 mL) was injected from the buccal aspect, 2–3 mm apical to the papilla tip, at a 45° angle. A single

puncture per session was used to minimize trauma. Slight blanching indicated correct placement. Each papilla received three injections at baseline, week 3, and week 6.

Participants avoided mechanical oral hygiene for 24 hours and interdental brushes for one week, replacing them with 0.12% chlorhexidine rinses. Modified Bass brushing resumed the following day.

Standardized photographs were obtained using a custom photograph standardization device (PSD), enabling consistent image acquisition. Black triangle height (BTH), width (BTW), area (BTA), and papilla height (PH) were measured at baseline, 1 month, and 3 months using ImageJ. PPI was recorded visually. Radiographs were taken to measure the distance between the interdental bone crest and contact point (IBC-ICP). Keratinized tissue thickness (KTT) was measured at baseline.

Pain was assessed after each injection using a VAS scale from 0 (none) to 10 (worst). Aesthetic satisfaction was rated at each visit using a VAS scale from 0 (not satisfied) to 10 (highly satisfied).

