## Statistical Analysis Plan

The data were analysed using the Statistical Package for the Social Sciences (SPSS) version 26.0. The normality of distribution for the numerical variables related to the patients and the evaluated interdental papilla sites was assessed based on skewness and kurtosis values. Normality of continuous data will be assessed using the Shapiro–Wilk test and visual inspection of Q–Q plots. A reference range of  $\pm 1.96$  was adopted as the criterion for normal distribution (Kalayci, 2005).

For each material, changes over time from baseline to follow-up will be analysed using repeated-measures ANOVA when assumptions are met, or the Friedman test in the case of non-parametric or ordinal data. Post-hoc pairwise comparisons between time points will include Bonferroni adjustments. Since the study design is split-mouth, inter-group comparisons between HA and i-PRF at each time point, as well as comparisons of change scores, will use paired t-tests for normally distributed variables and Wilcoxon signed-rank tests otherwise. PPI, being ordinal, will be evaluated with non-parametric paired procedures. Subgroup analyses will be performed separately for maxillary and mandibular papillae using similar paired or repeated-measures methods. Patient-reported VAS outcomes will be analysed using repeated-measures methods for within-group changes and paired testing for between-group differences.

Comparisons of KTT and IBC-ICP measurements across jaw localizations and treatment groups, as well as intergroup analyses of clinical outcome variables, were performed using the One-Way ANOVA test. Intragroup comparisons of variables measured at different time points were conducted using the Repeated Measures ANOVA. Where applicable, Post Hoc tests were employed to further investigate significant intergroup differences.

Additionally, to evaluate the relationship between KTT and IBC-ICP measurements and the percentage changes in clinical parameters, the Spearman correlation test was used. In interpreting the correlation coefficients, a range of 0.00–0.30 was considered low, 0.30–0.70 moderate, and 0.70–1.00 high. A significance level of  $p < 0.05$  and  $p < 0.01$  was adopted for all statistical analyses.

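### Material is randomised by side, but a left-right pair is not guaranteed, midline papillae have no allocation rule and the SAP defines no pairing unit; the HA versus i-PRF comparison should be made at side level

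*Combined protocol and SAP*

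**What the plan says.** In the combined protocol and SAP, the Study design section describes "13 systemically healthy adults with a total of 65 papilla deficiencies in the aesthetic zone". It requires at least two "papillae classified as Papilla Presence Index (PPI) class 2 or 3", with no condition on side, jaw or matching position. The listed exclusions that bear on the site itself are found in "Exclusion criteria included PPI class 4, diastema, active periodontal disease, smoking" and, later in the same list, previous surgical papilla reconstruction. None of them removes papillae on the midline. Allocation is by side: "one side was randomly assigned HA and the contralateral side i-PRF". Nothing is said about a site that lies on neither side.

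The Statistical Analysis Plan section takes its between-material tests from this design: "Since the study design is split-mouth, inter-group comparisons between HA and i-PRF at each time point", together with comparisons of change scores, "will use paired t-tests for normally distributed variables and Wilcoxon signed-rank tests otherwise". For the ordinal index, "PPI, being ordinal, will be evaluated with non-parametric paired procedures". Paired or repeated-measures methods are also planned separately for upper-jaw and lower-jaw papillae. The next paragraph of the same section says that One-Way ANOVA was used for intergroup analyses of the clinical outcomes. The section defines no pairing unit, no averaging within side and no handling of unmatched sites.

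**The concern.** A paired test needs a defined pair. Two kinds are possible here: two papillae, one from each side, or two sides of one participant. The SAP does not choose between them.

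- If the pair is two papillae, the rules do not produce complete pairs. Someone must decide which papillae to match and which to drop, possibly after seeing the data.
- If the pair is two sides, every participant needs at least one treated papilla on each side. Eligibility does not require this.
- The papilla between the two central incisors lies on neither side. This is anatomy; the documents do not discuss it. Randomising sides does not by itself determine the material for such a site, and the documents do not specify how it would be determined. Including such sites could bring non-randomised material into a randomised comparison.
- One-Way ANOVA does not solve the problem. It treats HA and i-PRF measurements as independent, although both come from the same mouths and several sites can share a side. Ignoring the shared mouth tends to lose precision, and ignoring clustering within a side tends to overstate it. The documents do not allow the net effect to be judged.

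**Working it through.** **Inputs.** 13 participants, 65 papillae, a minimum of two papillae per participant and allocation by side (all from Study design); paired tests and One-Way ANOVA (Statistical Analysis Plan). The plan gives no sample-size or power figure, so there is none to reproduce. It does not define the aesthetic zone, so the zones below are assumptions.

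**Step 1: counting pairs.** The mean is 65/13 = 5.0 papillae per participant. Pairs form within participants, so a participant with an odd count leaves at least one papilla unmatched. If *o* participants have an odd count, the maximum number of pairs is (65 − *o*)/2. Because 65 is odd, *o* must be odd and lies between 1 and 13.

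- *o* = 1: (65 − 1)/2 = 32 pairs, 1 site unmatched.
- *o* = 13, for example exactly five each: (65 − 13)/2 = 26 pairs, 13 sites unmatched (13/65 = 20%).

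These are upper limits on pairs. They assume that sites are split between the sides as evenly as possible and that every site has a side.

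**Step 2: participants with no left-right pair.** Suppose a zone has *l* left, *r* right and *m* midline sites, and a participant has *k* deficient papillae, every set of *k* sites being equally likely. The share of sets with no left-right pair is

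[C(*l*+*m*, *k*) + C(*r*+*m*, *k*) − C(*m*, *k*)] / C(*l*+*r*+*m*, *k*).

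| Assumed zone | *l*/*r*/*m* | *k* = 2 (eligibility minimum) | *k* = 5 (trial mean) |
|---|---|---|---|
| One arch, canine to canine, no midline | 2/2/0 | 2/6 = 33% | not possible |
| Both arches, canine to canine, no midline | 4/4/0 | 12/28 = 43% | 0/56 = 0% |
| One arch, canine to canine | 2/2/1 | 6/10 = 60% | 0/1 = 0% |
| One arch, first premolar to first premolar | 3/3/1 | 12/21 = 57% | 0/21 = 0% |
| Both arches, canine to canine | 4/4/2 | 29/45 = 64% | 12/252 = 4.8% |
| Both arches, first premolar to first premolar | 6/6/2 | 55/91 = 60% | 112/2002 = 5.6% |

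At five papillae each, the expected number of participants without a left-right pair is at most 13 × 0.056 = 0.7. The shares are counts of permitted configurations, not estimates of what happened.

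**Step 3: jaw subgroups.** A paired test within a jaw needs both sides of that jaw. With both arches canine to canine and two papillae, 2 × (2 × 2) = 8 of 45 sets contain such a pair. One papilla on each side of the mouth is therefore not enough for the planned subgroups.

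**The case against.** The strongest reply is that a split-mouth trial with five papillae per participant will nearly always have both sides represented, and that a paired test on side means needs only one treated papilla per side. On that reading the odd total is harmless. Most of this stands: the odd total rules out complete matching of papillae, but not a paired analysis of participants. What does not stand is that the plan already says so. Side means are not specified, and eligibility does not ensure both sides.

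Three stronger readings are tempting and are not supported.

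- A reader might infer that a third to two thirds of participants had no pair. The 33-64% range applies only to someone with exactly two papillae. At the trial's mean the same assumption gives about 0-6%. The distribution per participant is not given, so some may have had two, but nothing shows it.
- A reader might infer that the operator chose the material for midline papillae. The documents never mention midline papillae, neither how many were treated nor how their material was set. Their allocation is unspecified; that is all that can be said.
- A reader might infer that 20% of sites were midline, from five papillae in one arch per participant. The planned upper-jaw and lower-jaw subgroups show that the sites did not all come from one arch type, and nothing says that each participant contributed a full anterior arch.

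It may also be said that One-Way ANOVA needs no pairs, so the paired problem falls away. It does for the mechanics of that test, but the test discards the design feature that justifies a split-mouth trial, and it contradicts the paired plan in the preceding paragraph.

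**Conclusion.** The concern holds as a gap in the analysis plan. It is certain from the text that no pairing unit is defined, that a left-right pair is not required for entry, that no rule covers midline sites, and that at least one of the 65 papillae has no one-to-one partner. The SAP's paired tests therefore cannot be run on all sites without ad hoc matching or dropping, and the alternative it names ignores the pairing.

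The realised size is unknown. At site level, the ceiling on pairs is 26 to 32, depending on how many participants had an odd count. At participant level, the likely loss is less than one of 13 if all had about five papillae and sites were equally likely to be affected; each participant lost would remove 1/13 = 8% of the pairs. How much midline sites matter cannot be judged until they are counted.

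**What to change.** In the Statistical Analysis Plan, replace site-level paired tests and One-Way ANOVA for the HA versus i-PRF comparison with one of the following:

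- a paired t-test or Wilcoxon signed-rank test on each participant's HA-side mean and i-PRF-side mean (up to 13 pairs); or
- a mixed model on papilla-level data with material as a fixed effect and random effects for participant and for side within participant.

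Both respect the unit that was randomised and accept unequal numbers of papillae per side. The jaw subgroups should use the same approach within jaw, stating how many participants have both sides represented there.

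Report left, right and midline counts per participant and jaw, and how any midline papilla received its material. Where side randomisation did not determine the material, leave the site out of the randomised comparison, or show results with and without it.

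Study design is written as if enrolment were complete. Only if it is still open is it useful to add to the inclusion criteria that at least one qualifying papilla is needed on each side of the midline.

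The cost is a few sentences of SAP text and one table. The downside is that a participant with sites on only one side, and any midline sites with non-randomised material, contribute little or nothing to the comparison between materials.

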# Study Protocol with Statistical Analysis Plan

## Scientific Background

Loss of the interdental papilla is a frequent aesthetic concern, particularly in the anterior region where even minor deficiencies create visible black triangles. These deficiencies contribute to plaque accumulation, food impaction, and phonetic disturbances, in addition to compromising smile harmony. Earlier attempts to reconstruct missing papillae through surgery often yielded unpredictable outcomes, largely due to the delicate blood supply of the papillary region. As a result, attention has shifted toward non-surgical injectable biomaterials designed to restore soft-tissue volume with minimal invasiveness.

Hyaluronic acid (HA) dermal fillers have become widely used in aesthetic and periodontal therapy due to their biocompatibility, hydrophilicity, and ability to stimulate wound healing. Clinical studies have consistently reported partial or complete closure of black triangles following repeated HA injections. Injectable platelet-rich fibrin (i-PRF), prepared via low-speed centrifugation, represents an autologous alternative that provides a fibrin scaffold enriched in platelets and leukocytes. Its gradual release of growth factors promotes angiogenesis, fibroblast proliferation, and extracellular matrix formation.

Despite increasing interest, direct comparisons between these two materials are scarce, and previous trials have not used a split-mouth design to minimize interpatient variability. This study directly compares HA and i-PRF administered under identical intraoral conditions. We hypothesized that both would yield significant improvement in papilla fill without clinically meaningful differences between them.

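### Apart from injection pain, no adverse event is defined, recorded by side or analysed over about 195 injections, and blanching is noted only as a sign of placement

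*Combined protocol and SAP*

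**What the plan says.** The trial "included 13 systemically healthy adults with a total of 65 papilla deficiencies in the aesthetic zone". Allocation is within the mouth: "For each participant, one side was randomly assigned HA and the contralateral side i-PRF". On exposure, the Study design section says "Each papilla received three injections at baseline, week 3, and week 6", and that a single "puncture per session was used to minimize trauma".

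The same section lists what is collected:

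- black triangle height, width and area, and papilla height, from standardised photographs at baseline and at one and three months;
- the Papilla Presence Index;
- the radiographic distance from bone crest to contact point;
- keratinized tissue thickness at baseline;
- a pain VAS after each injection;
- a satisfaction VAS at each visit.

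The Statistical Analysis Plan analyses these measures and no others. It includes paired testing of the patient-reported VAS scores between materials.

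On perfusion, the Study design section says only "Slight blanching indicated correct placement". The Scientific Background attributes the unpredictable results of earlier papilla surgery "largely due to the delicate blood supply of the papillary region". The stated hypothesis is: "We hypothesized that both would yield significant improvement in papilla fill without clinically meaningful differences between them".

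**The concern.** This is a head-to-head comparison of a commercial filler and an autologous product, and the sponsor expects them to perform alike on papilla fill. If they do, tolerability becomes one of the main grounds for choosing between them. The plan measures one aspect of it, pain at injection.

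Swelling, haematoma, infection, ulceration, nodules and lasting colour change have no definition, no form and no table. Blanching is observed at the chair but is not an item of data, so the record cannot separate blanching that cleared from blanching that did not.

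A split-mouth design is well suited to local reactions, because each participant acts as their own control. Without recording by side that advantage is lost. A reaction that has cleared cannot be recovered later from photographs taken at one and three months.

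**Working it through.** **Inputs.** From the Study design section: 13 participants, 65 papillae, three sessions, one puncture per session, one side per material. The documents give no total injection count, no expected event rate and no sample-size calculation, so there is no stated figure to reproduce.

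**Exposure.**
- Injections: 65 papillae × 3 sessions × 1 puncture = 195, or 195 / 13 = 15 per participant on average.
- Reading the sentence as three injections at every session would give 65 × 9 = 585. The single-puncture statement rules that out.
- Side-sessions per material: 13 × 3 = 39, assuming every participant is treated on both sides, as the allocation sentence implies.
- Injections per material: 195 / 2 = 97.5, so 97 or 98 if the sides are balanced. This is an assumption; the split by side is not given.

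**What is recorded about harm over that exposure.**

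| Type of harm | Recorded? | Compared between materials? |
|---|---|---|
| Pain at injection | Yes, VAS after each injection | Yes, paired test |
| Lasting tissue loss | Indirectly, through papilla height, black triangle area and the papilla index | Yes, as efficacy outcomes |
| Swelling, haematoma, infection, ulceration, nodule | No | No |
| Blanching that persists | No | No |

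**What recording by side could show.** The unit is the participant-side, n = 13 per material.

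- Upper limit with no events, one-sided 95%: 1 − 0.05^(1/13) = 0.206, or 20.6%.
- Upper limit with no events, two-sided 95%: 1 − 0.025^(1/13) = 0.247, or 24.7%.
- Treating 97 injections as independent would give 1 − 0.05^(1/97) = 0.030, or 3.0%. That is too optimistic, because injections cluster within participants.
- Chance of seeing at least one event on a given side, 1 − (1 − p)^13, at assumed participant-level rates p:

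| Assumed rate p | Chance of at least one event |
|---|---|
| 1% | 12% |
| 2% | 23% |
| 5% | 49% |
| 10% | 75% |

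- Exact paired test with d discordant participants, all in one direction: two-sided p = 2 × 0.5^d. For d = 5 this is 0.0625 and for d = 6 it is 0.031. At least 6 of 13 participants would have to react on the same material's side only before the test fell below 0.05.

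**The case against.** Several objections limit the point.

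**Some harm is measured.** A reader might infer that the plan collects no harm at all. It does not support that. Pain is scored after each injection, each injection belongs to one material, and a paired test is planned. The comparison is weak, because every site has infiltration anaesthesia and the plan does not say how scores are assigned to a side if both are treated at one visit. It is planned nonetheless.

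**Lasting tissue loss would not go unseen.** If still present at one or three months, it would lower papilla height, enlarge the black triangle area or worsen the papilla index. It would count as an efficacy result and not as a reported event, but it is measured.

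**The blood-supply and blanching statements do not conflict.** A reader might set "largely due to the delicate blood supply of the papillary region" against "Slight blanching indicated correct placement" and see a contradiction. The first explains why surgery was unpredictable, and the text then gives this as the reason for moving to injectables. The second concerns needle technique and is already limited to slight blanching. The gap is only that persistence is not recorded.

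**The hypothesis claims no overall equivalence.** It is worded for papilla fill, and nowhere does the plan claim equal safety. A wider reading is a risk in how the results are used, not a statement in the plan.

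**Thirteen pairs cannot settle safety.** This stands in full. It argues for descriptive reporting with its limits shown. It does not argue for recording nothing.

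**The trial may be over.** Much of the Study design section is in the past tense. If treatment is complete, new forms are of no use and only retrospective abstraction and disclosure remain.

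**Conclusion.** The concern holds in this form: apart from the pain VAS, no adverse event is defined, recorded by side or analysed over about 195 injections (39 side-sessions per material), and whether blanching persisted is not recorded. A trial run exactly as written would yield no count of local reactions by material.

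The documents do not show that any harm occurred, that safety is wholly unmeasured, or that their sections contradict one another. Nor would the remedy give a reliable safety comparison, since a clean record in 13 participants is still compatible with a true rate of up to about 21% (one-sided 95%).

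The conclusion rests on the document as supplied, on one injection per papilla per session, and on every participant being treated on both sides. The event rates used above are assumptions. The change should be made, because it alters what is collected and reported at little cost.

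**What to change.** 1. **Add a one-page checklist by side**, completed at the three existing injection sessions and at the one- and three-month visits. Items: swelling, haematoma, infection, ulceration or necrosis, nodule, persistent blanching or colour change, and other.
2. **Add one descriptive table to the Statistical Analysis Plan**: events per participant-side by material, with exact confidence limits and no claim of a powered comparison. If no events are seen, print the upper limit (20.6% one-sided, 24.7% two-sided) beside the zero.
3. **State the scope of the conclusion**: any finding of no meaningful difference covers papilla fill and the other outcomes measured.
4. **If treatment is already complete**, abstract reactions by side from the clinical notes and state in the report that adverse events were not systematically collected.

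The cost is 3 + 2 = 5 pages per participant, so 13 × 5 = 65 pages in all, a few minutes at each visit, and one table. No extra visits or contacts are needed. Recording only at visits may under-count reactions that come and go between sessions, and the report should say so.

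### Pain and aesthetic satisfaction are scored by participants and compared between HA and i-PRF, but only the examiner is described as blinded, so an average preference for one material would enter the paired VAS difference

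*Combined protocol and SAP*

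**What the plan says.** Allocation is within the mouth: "For each participant, one side was randomly assigned HA and the contralateral side i-PRF". The Study design section names one blinded party: "Outcome assessments were performed by a blinded examiner". It does not mention masking of participants or of the operator, or hiding the preparation or the syringes.

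On the i-PRF side, "For i-PRF sites, 10–20 mL of venous blood was collected into plastic tubes and centrifuged at 700 rpm for 3 minutes", and then "The upper orange plasma layer was aspirated and transferred to 1-mL insulin syringes". The injection step is the same for both materials: "HA or i-PRF (0.1–0.2 mL) was injected from the buccal aspect, 2–3 mm apical to the papilla tip, at a 45° angle". The appearance of the HA and of its syringe is not described.

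Pain is scored from 0 to 10 after each injection, and satisfaction is scored as follows: "Aesthetic satisfaction was rated at each visit using a VAS scale from 0 (not satisfied) to 10 (highly satisfied". The Statistical Analysis Plan makes the participant the source of both scores and sets the comparison: "Patient-reported VAS outcomes will be analysed using repeated-measures methods for within-group changes and paired testing for between-group differences".

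**The concern.** For the two VAS outcomes the participant is the assessor, so blinding the examiner gives these scores no protection. If participants learn which side received which material, any expectation they hold about it can influence both ratings.

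The split-mouth design removes what a person brings to both sides, such as a habit of scoring high. A preference for one material is a difference between sides, so it stays in the within-person difference. Randomising the side does not help, because the preference follows the material and not the side. The average preference across participants therefore shifts the mean of the paired differences.

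At stake is the between-material reading of pain and satisfaction. A shift could create an apparent difference, or it could hide a real one.

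**Working it through.** **Does the described blinding cover the VAS scores?**

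- Blinded party: the outcome examiner (Study design).
- Assessor for pain and satisfaction: the participant (Statistical Analysis Plan, which calls them patient-reported).
- Assessor for the ImageJ measures and PPI: the examiner, as outcome assessor.

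The described blinding covers the last group and not the VAS scores.

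**Which cues could reveal the side?**

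- The blood draw alone does not. Every participant has one i-PRF side, so everyone is bled whichever side was allocated.
- The colour and syringe of the i-PRF might, if the participant sees them and HA looks different.
- The need to inject i-PRF within 5 minutes of preparation might, if the order or timing is visible.
- Being told would. The plan does not say what participants are told.
- Anaesthesia, volume range, site and angle are the same for both materials, so the described technique is not a cue. Whether the materials feel different on injection is not stated.

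**How much could a preference matter?**

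The plan gives no VAS standard deviation, effect size or sample-size calculation, so there is no figure of its own to reproduce. What follows is an illustration.

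Inputs from the documents:

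- "This randomized split-mouth clinical trial included 13 systemically healthy adults with a total of 65 papilla deficiencies in the aesthetic zone", taken here as 13 pairs with one summary score per side for each participant.
- Significance levels 0.05 and 0.01 (Statistical Analysis Plan). Sidedness is not stated; two-sided is assumed.

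Assumed inputs:

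- True difference between materials: zero.
- SD of the paired VAS difference, s: 1.5 to 2.0 points.
- Average preference for one material, b: 0.5 or 1.0 point.

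The paired t statistic then follows a noncentral t distribution with 13 − 1 = 12 degrees of freedom and noncentrality λ = (b / s) × √13. The false-positive rate is P(|T| > c), with c = 2.179 at 0.05 and c = 3.055 at 0.01.

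| b (points) | s (points) | b / s | λ | Rate at 0.05 | Rate at 0.01 |
|---|---|---|---|---|---|
| 0 | any | 0 | 0 | 5.0% | 1.0% |
| 0.5 | 2.0 | 0.250 | 0.901 | 13.2% | 3.7% |
| 0.5 | 1.5 | 0.333 | 1.202 | 19.8% | 6.3% |
| 1.0 | 2.0 | 0.500 | 1.803 | 38.2% | 15.6% |
| 1.0 | 1.5 | 0.667 | 2.404 | 59.8% | 31.0% |

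A smaller average preference of 0.3 point gives 7.9% (s = 2.0) to 10.2% (s = 1.5) at the 0.05 level.

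**The case against.** The strongest objection is that the plan is silent about participants, and silence is not evidence that they were unmasked. A reader might infer that participants could see which side received their own blood product. The documents do not say so: they do not report what participants saw or were told, they do not describe the HA syringe, and the consent pages were not available for this review. This stands. The supportable statement is that participant masking is not described and that the materials may be distinguishable.

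A reader might also infer that the SAP treats the scores as masked. It says nothing on that, and a paired test is the right form for within-person data, masked or not. The test is not at fault; what its result can be taken to mean is.

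The size is assumed. Neither the preference nor the SD comes from the documents. Only the average preference moves the test: if some participants favour their own blood product and others the filler, the shifts partly cancel and the spread widens. This stands, and the table should be read as showing sensitivity, not as an estimate. The rates are also lower at the 0.01 level.

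It would be too strong to say that the gap is easy to close. Sleeved syringes hide colour but not any difference in feel.

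Finally, the Study design is written in the past tense, so treatment may be complete and masking no longer possible. The stated hypothesis concerns papilla fill, not VAS. Both points limit the scope, but neither removes the pre-specified VAS comparison or the need to say how it should be read.

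**Conclusion.** The concern holds in limited form. As written, the plan protects the examiner's assessments by blinding and describes no equivalent protection for the two patient-reported outcomes, although it compares the materials on both. A preference shared in one direction would bias those comparisons, and neither the pairing nor the randomisation of sides would remove it.

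Under the stated assumptions, an average preference of 0.5 point raises the false-positive rate from 5% to 13–20%, and 1.0 point raises it to 38–60%. At the 0.01 level, the rate rises from 1% to 4–6% and 16–31%. These figures depend on the assumed SD and preference, on 13 pairs and on two-sided testing.

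The documents do not show that participants were in fact unmasked, or that any such preference existed. The comparisons of ImageJ measures and PPI are not exposed by this route.

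**What to change.** If injections are still to be given, state in the Study design that:

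- participants are not told which side receives which material;
- both materials are prepared out of the participant's view and given from sleeved syringes;
- pain and satisfaction are each recorded for the right and left side, and not by material;
- participants are asked which side they think received i-PRF, soon after an injection session, and the guesses are reported beside the VAS results. A late question is a weaker check, because the answer may reflect which side looks better.

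The plan should also say whether the operator was masked.

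The cost is sleeves and one extra question, with no added staff or visits. The set-up becomes slightly slower and has to fit the 5-minute window stated for i-PRF. Masking may remain incomplete if the materials feel different on injection, and the guess data would help to show this.

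If treatment was given without masking, say so, label the between-material VAS comparisons as unblinded and exploratory, and do not use them to support a claim of either difference or similarity between the materials. That costs a sentence in the SAP and one in the report.
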